7.3. Demographic and Baseline Characteristics

Demographics variables will include: age, sex, ethnicity and race. For summary purposes, age will be derived by comparing date of birth to date of informed consent.

Baseline characteristics will include: relevant medical history, wart history (including prior treatment), Fitzpatrick Skin Type, height, weight and body mass index (BMI). BMI will be calculated by weight (kg) / height (m²). Wart history variables that will be summarized include time since clinical diagnosis (as compared to informed consent), age at clinical diagnosis and any previous treatments for warts. Time since clinical diagnosis will be derived by comparing the date of informed consent to date of clinical diagnosis. Time since clinical diagnosis will be expressed in months using the following conversion: (12 * days) / 365.25. In the event the date of clinical diagnosis is not complete (“partial date”), the date will be imputed with the earliest date possible. As an example, if only the month and year are known for date of clinical diagnosis, the first day of the month will be used for imputation purposes.

Age at clinical diagnosis will be derived by comparing date of clinical diagnosis to date of birth. Incidence of the following prior wart treatment categories will be tabulated: Cantharidin, Anti-Virals, Retinoids, Salicylic Acid, Curettage, Freezing, Other. Relevant medical history will not be summarized in a table but will be displayed in a listing.

Continuous variables will be summarized using descriptive statistics. Categorical variables will be summarized using counts and percentages. Demographics, baseline characteristics, wart history and prior wart treatment will be summarized for all 3 analysis populations (ITT, Safety, Per Protocol).

8. Efficacy Analysis

The ITT and Per Protocol population will be used for efficacy analysis. Analyses based on the ITT population will be considered the primary analyses. Results will be summarized using descriptive statistics and counts/percentages. For select endpoints, 95% confidence intervals may be generated as well.

On the Wart Location and Measurement case report form (CRF), wart information is collected for each individual wart. For the purpose of efficacy analysis, clearance of each wart needs to be determined using results collected on this page. A wart will be considered to have cleared for a particular visit when a wart is reported to have a diameter of 0 mm at that visit. Should a wart return after initial clearance, a diameter > 0 mm will be recorded, and the wart will not be considered cleared at that visit. Otherwise,

if the wart does not return, the check box “Wart has cleared” will be marked for subsequent visits. For the purpose of analysis, the wart will be counted as cleared at all visits where “Wart has cleared” has been marked.

Some efficacy endpoints will be summarized by treatment visit. Treatments are planned to occur every 21 days as long as warts are present for up to 4 treatments within the 75 day treatment period. Treatment may be delayed for various reasons including, but not limited to, ongoing local skin reactions (e.g. scabbing). As a result, the timing of when subjects receive treatment may vary. For the purpose of naming treatment visits, only visits when treatment was given or the check box “Wart has cleared” for all warts will be considered. Using this method, Treatment Visit 1 will be the 1st visit treatment was applied; Treatment Visit 2 will be the 2nd visit treatment was applied, etc. Visits when treatment was planned to be given but treatment was not applied or clearance was not achieved will be recorded as “Unscheduled”.

For results to be considered for any by visit analyses, visits must be within visit windows as described in this section of the analysis plan. Results that are collected between Day 11 and Day 157 will be assigned to visits according to the visit windows described below, regardless of the name of the visit. Should two or more results be collected within a specific visit window, the visit closest to the planned day with a non-missing value will be used for analysis. Results from visits that occur outside the visit windows will not be considered for analysis, but will be included in study listings. The visit windows to be considered are as follows:

- Day 21- visit falls +/- 10 days from planned visit study day (i.e., between Day 11 and Day 31)
- Day 42- visit falls +/- 10 days from planned visit study day (i.e., between Day 32 and Day 52)
- Day 63- visit falls +/- 10 days from planned visit study day (i.e., between Day 53 and Day 73)
- End of Treatment (EOT) Visit- visit falls +/- 10 days from planned visit study day (i.e., between Day 74 and Day 94)
- Day 105- visit falls +/- 10 days from planned visit study day (i.e., between Day 95 and Day 115)
- Day 126- visit falls +/- 10 days from planned visit study day (i.e., between Day 116 and Day 136)
- Day 147- visit falls +/- 10 days from planned visit study day (i.e., between Day 137 and Day 157)

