- b. Subjects are to be scheduled in 21-day intervals (+/- 4 days) after each treatment for subjects in Cohort 2. The next Treatment Visit is to be scheduled 21 (+/- 4 days) after the last treatment, but only after any LSR has resolved sufficiently to allow evaluation of the treatment site. The research team should be in contact with the patient until LSRs are resolved and a treatment visit can be scheduled within 21 days (+/- 4) when possible. The 24-hour phone contact may be conducted at +/- 6 hours. The 7-day phone contact may be conducted +/- 24 hrs.
- c. A final in person safety assessment, ERT, photos and study completion form will be completed at the Day 147 (EOS) Visit for all subjects. EOS conducted outside the Day 147 EOS visit window will be considered a protocol deviation. Treatments may be administered up to Day 75 in Cohort 2. Subjects in Cohort 2 are to attend all visits whether they have achieved complete clearance prior to and at the Day 84 (- 0/+ 8 days) EOT assessment.
- d. Demographics: date of birth, sex, race/ethnicity will be collected.
- e. Vital signs (e.g., temperature & heart rate) will be obtained at each treatment prior to application of Study drug. Height and weight will be collected at Screening/Day 1, EOT Day 84 (- 0/+ 8 days) and subsequent follow up visits Day 105, 126 and 147 (EOS).
- f. Limited physical examination. Symptom or AE-directed physical examination may be performed if warranted. (See Source/eCRF for a more detailed description)
- g. Dermatologic exam including Fitzpatrick Skin Type, location of each wart is identified and documented on the body map and source as outlined in the MOP. Measurements of warts should be recorded on Day 1 prior to treatment to confirm they meet inclusion criteria of ≤ 10 mm in diameter and ≤3 mm in height. Wart location, measurements and assessments are to be completed prior to each treatment application and/or each in-person visit. New warts should be recorded in the corresponding Source/eCRF. Instructions for measuring and documenting the and measurements are provided in the Manual of Operations.
- h. Paring at first visit by Dermatologist or qualified designee. Paring at additional treatment visits if significant hyperkeratosis or at Investigator’s discretion.

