It can sometimes be challenging to determine if a wart is completely clear after treatment due to ongoing local skin reactions. At any visit where the investigator is unable to evaluate or treat some warts due to ongoing local skin reactions, an "Unscheduled" Visit should be documented. The timing of the next visit will be determined by the resolution of the local skin reaction. A Treatment Visit should be documented at every visit where Study drug is applied. Treatment should only take place at a visit when all warts are evaluable (i.e., not obscured by an ongoing LSR) and all warts that are not completely clear, should undergo treatment with Study drug. No partial treatment of warts is permitted.

For Cohort 2, Study drug is to be applied to the wart site on any Treatment Visit where a new clinical assessment of complete clearance is made for that wart (*e.g., if a patient returns for Treatment Visit 2 and is clinically assessed to have no visible evidence of remaining wart, then Study drug is to be applied to this wart site at Treatment Visit 2. However, if the patient remains completely clear at that wart site when returning for Treatment Visit 3, then no Study drug would be applied at Treatment Visit 3.*) Should it become clear that the subject will be unable to complete the EOS visit within the allowed window of Day 84 (- 0/+ 8) days, the subject should be brought in for their EOS visit as soon as they are able. This will be documented as a protocol deviation.

In instances where the clinician can adequately assess the treatment sites but is uncertain if residual wart is remaining, treatment should be applied, and the subject should return for evaluation per protocol. Treatment visits and assessments are to take place in order (e.g., Treatment 1, Treatment 2, Treatment 3 and Treatment 4). Subjects that receive fewer than 4 treatments within the 63-day (Cohort 1) or 75-day (Cohort 2) treatment period, due to the duration of post-treatment local skin reactions, will not be considered a protocol deviation. No treatment should be administered after the 63-day treatment period in Cohort 1 or the 75-day treatment period in Cohort 2 without Sponsor's approval.

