9.2.7 Handling of Missing data

Clearance of all treatable warts is to be assessed at each Treatment Visit as well as unscheduled visits over the duration of the study. The assessment done at the EOS Visit (Day 84) will be considered to be the primary efficacy endpoint.

Subjects who do not have an assessment of complete clearance of all treatable warts at the EOS Visit (Day 84) will be considered to have missing data for the primary endpoint. The primary method to handle missing data will be to assign all subjects with missing complete clearance data as not having achieved complete clearance.

The procedures for handling missing data for other study endpoints will be described in the statistical analysis plan.

9.3 Informed Consent/Assent and Authorization for Use and Disclosure of Protected Health Information

Written assent and informed consent and authorization of use and disclosure of protected health information must be obtained from each subject (or the subject's legally acceptable representative) before performing any study-specific screening/baseline period evaluations. One copy of the signed informed consent form (and IRB-required assent form) and authorization for use and disclosure of protected health information form will be given to the subject, and the investigator will retain the original. The informed consent/assent form and authorization for use and disclosure of protected health information, which is prepared by the investigator or the site, must have been reviewed and approved by the sponsor, the study monitor, and the investigator's IRB and privacy board (if separate from the IRB) before the initiation of the study. The informed consent form must contain the 20 elements of informed

consent described in International Council for Harmonisation E6, Section 4.8. The authorization for use and disclosure of protected health information must contain the elements required by Title 45 of the Code of Federal Regulations, Section 164.508(b), and any local regulations for valid authorizations.

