8.4.1. Handling of Missing Data for Complete Clearance Endpoint

The efficacy endpoint, proportion of subjects exhibiting complete clearance of all treatable warts, is to be assessed during the study. Assessments are to be done at Treatment Visit 2, Treatment Visit 3, Treatment Visit 4, the EOT visit and follow-up visits at Day 105, Day 126 and Day 147.

Subjects who do not have an assessment of complete clearance of all treatable warts in a particular visit window for any of the scheduled assessments will be considered to have missing data for this endpoint at that visit. The primary method to handle missing data will be to assign all subjects with missing clearance data as not having achieved complete clearance. For additional considerations related to assessments of clearance, see Section 8 (Efficacy Analysis).

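### The SAP's Day 74–94 EOT window lets a pre-dose clear reading from a Day 74–75 Treatment Visit become the primary result when nothing nearer Day 84 exists, contrary to protocol 9.2.7

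*SAP*

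**What the plan says.** SAP Section 8 sets seven adjoining analysis windows. The one for the primary time point is "End of Treatment (EOT) Visit- visit falls +/- 10 days from planned visit study day (i.e., between Day 74 and Day 94". Results are "assigned to visits according to the visit windows described below, regardless of the name of the visit". If several results fall in one window, the non-missing one nearest the planned day is used; no rule for ties is given. SAP 8.4.1 defines missing by the window: "Subjects who do not have an assessment of complete clearance of all treatable warts in a particular visit window" are the ones treated as missing, and they are scored not cleared.

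Protocol 9.2.7 defines missing by the visit. It notes that clearance is assessed at Treatment Visits and unscheduled visits too, but makes the Day 84 assessment the primary endpoint. Those with missing data are "Subjects who do not have an assessment of complete clearance of all treatable warts at the EOS Visit (Day 84"), and "The primary method to handle missing data will be to assign all subjects with missing complete clearance data as not having achieved complete clearance". For Cohort 2 the Day 84 visit is the EOT visit, which protocol 4.1 schedules at Day 84 −0/+8.

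Three protocol rules make the overlap matter:
- Table 2, footnote c: "Treatments may be administered up to Day 75 in Cohort 2".
- Table 2, footnote g: "Wart location, measurements and assessments are to be completed prior to each treatment application and/or each in-person visit".
- Section 4.1, among its Cohort 2 rules: "Study drug is to be applied to the wart site on any Treatment Visit where a new clinical assessment of complete clearance is made". A visit recorded as fully clear can therefore also be a dosing visit.

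**The concern.** The analysis window opens on Day 74, while dosing is still permitted. A reading taken just before the last application can therefore be reported as the end-of-treatment outcome. If the subject never attends the EOT visit, the two documents score the same subject in opposite ways in the primary ITT analysis. That error can only raise the clearance rate.

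If the EOT visit is held on Day 95 or later (protocol 4.1 has late subjects brought in when they can attend, as a deviation), it falls into the Day 105 window. The pre-dose reading then stands in its place, and the error can go either way.

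The protocol synopsis intends these rates to inform assumptions for later placebo-controlled trials. The SAP rule is explicit enough to be programmed exactly as written.

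**Working it through.** **Inputs from the documents.** EOT analysis window Day 74–94 (SAP 8). Last dosing day 75 without sponsor approval (protocol Table 2, footnote c). Treatment interval 21 ± 4 days, i.e. 17–25 (footnote b). EOT visit Day 84 −0/+8, i.e. Day 84–92 (protocol 4.1). About 35 subjects (SAP 4).

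**Assumptions, not in the documents.** All permitted interval combinations equally likely. No EOT visit in 10–20% of subjects. Recorded clear before dosing in 30–60%. These conditions are independent of one another.

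**1. The plan's own window.** 84 − 10 = 74 and 84 + 10 = 94, as stated. The neighbouring windows are Day 53–73 and Day 95–115, so no day is unassigned. The overlap with permitted dosing is Days 74 and 75.

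**2. Can Treatment Visit 4 fall there?** Its day is the origin plus three intervals. Table 2 calls the first treatment Day 1, whereas the SAP's planned Days 21, 42 and 63 fit a count from Day 0, so both are shown. The range is Day 52–76 (Day 1 origin) or Day 51–75 (Day 0 origin). With a maximum interval of 25 days, a total that falls short of 75 by s days arises in (s+1)(s+2)/2 ways: 1, 3 and 6 for s = 0, 1 and 2.
- Day 1 origin needs a total of 73 or 74: 6 + 3 = 9 schedules.
- Day 0 origin needs a total of 74 or 75: 3 + 1 = 4 schedules.
- Of 9³ = 729 schedules (17–25 days): 0.5% to 1.2%.
- Of 5³ = 125 schedules, if skin reactions push every interval to 21–25 days: 3.2% to 7.2%.

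**3. Which result is selected?** Day 74 is 10 days from Day 84 and Day 75 is 9 days away.

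| EOT visit held | Distance from Day 84 | Result used as EOT |
|---|---|---|
| Day 84–92 | 0–8 | EOT visit, in all 2 × 9 = 18 pairs |
| Day 93 | 9 | EOT visit against Day 74; tie with Day 75 |
| Day 94 | 10 | Tie with Day 74; Day 75 reading wins |
| Day 95 or later | outside window | Pre-dose reading |
| Not held | none | Pre-dose reading |

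In the last row, a clear reading gives cleared under the SAP and not cleared under protocol 9.2.7.

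**4. Size when no EOT visit is held.** Each affected subject moves the rate by 1/35 = 2.9 points. With p = P(Day 74–75) × P(no EOT visit) × P(clear), the expected number is 35p and the chance of at least one is 1 − (1 − p)^35.

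| Intervals | 35p | Mean shift (100p points) | Chance of at least one |
|---|---|---|---|
| 17–25, low | 35 × 4/729 × 0.1 × 0.3 = 0.006 | 0.02 | 0.6% |
| 17–25, high | 35 × 9/729 × 0.2 × 0.6 = 0.05 | 0.15 | 5% |
| 21–25, low | 35 × 4/125 × 0.1 × 0.3 = 0.03 | 0.10 | 3% |
| 21–25, high | 35 × 9/125 × 0.2 × 0.6 = 0.30 | 0.86 | 26% |

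For scale, on an assumed base of 14/35 = 40.0% (exact 95% interval 23.9–57.9), one extra subject gives 15/35 = 42.9% (26.3–60.6).

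**The case against.** The best case against: assigning results by study day is ordinary practice, and the nearest-day rule protects every on-time EOT visit. The SAP also keeps missing as not cleared. SAP 8.4 separately scores subjects who ask to leave because of study-related adverse events or spreading disease as failures. The study is descriptive, with no power basis and no comparisons. Three uncommon conditions must coincide, and two of their rates are assumed. All of this stands, and it makes the point minor. It does not remove the contradiction, because none of these safeguards covers a subject who misses the EOT visit for another reason.

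Stronger readings that the documents do not support:
- **That compliant EOT visits are overwritten.** A Day 74–75 reading never beats a visit on Day 84–92. An Unscheduled visit on Day 76–83 could in principle be nearer. However, Table 2 schedules no wart measurement at Unscheduled visits and SAP 9.1 sends their counts to listings. Protocol 9.2.7 does mention clearance assessment there, so a residual ambiguity remains, not a demonstrated error.
- **That the Per Protocol analysis is fully protected.** SAP Section 6 excludes subjects who do not return for the EOT visit. One who returns on Day 95 or later is not automatically excluded; that depends on the deviation review.
- **That protocol 8.2 already settles the matter by counting non-completers as failures.** That sentence sits under study or site termination. SAP 7.1 defines Cohort 2 study completion by the Day 147 visit, so read literally it would also fail a subject who was clear at EOT and left later.
- **That wart-count and wart-area endpoints share the error.** With no EOT visit, last observation carried forward (SAP 8.4.2) would bring forward the same pre-dose value anyway.

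**Conclusion.** The conflict is real but small. As written, the SAP can score as cleared, in the primary ITT analysis, a Cohort 2 subject whom protocol 9.2.7 scores as not cleared. With no EOT visit the error only raises the rate. With an EOT visit on Day 95 or later it can go either way.

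A reader might infer that the reported rate is materially inflated. The figures do not show that: the expected shift is below one point in every scenario, and the 26% chance of any affected subject needs every assumption at its upper end. Nor are these figures firm bounds. The enumeration stops at 25-day intervals, although treatment may wait longer for skin reactions to resolve. A delayed earlier treatment falling on Day 74–75, and EOT visits on Day 95 or later, are also not counted. The reason to act is that the rule is explicit and contradicts the protocol.

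**What to change.** In SAP Section 8 and 8.4.1, state that the primary clearance result at EOT comes only from the recorded in-person EOT visit, never from a pre-dose Treatment Visit or an Unscheduled visit. If no such assessment lies in the Day 74–94 window, apply the existing missing-as-not-cleared rule. This also removes the tie cases.

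Flag EOT visits outside the protocol's Day 84 −0/+8 window. Because protocol 9.2.7 does not say how an early or late EOT assessment should be scored, add a sensitivity count with EOT visits on Day 74–83 and after Day 94 scored the other way. SAP Section 3 gives the EOT visit window as ±8 days where the protocol gives −0/+8; the two must be reconciled.

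I would leave the Treatment Visit 2–4 endpoints alone here. They are named by treatment order but windowed by day. Switching to treatment number could create more imputed failures among subjects with fewer than four treatments.

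The cost is a few sentences before database lock and a minor programming change. The downside is that a few subjects may change to not cleared.

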8.1. Efficacy Variables

Primary endpoint:

- Proportion of subjects exhibiting complete clearance of all treatable warts (baseline and new) at the End of Treatment (EOT) Visit (Day 84).

Secondary endpoints:

- Change from baseline in the number of treatable warts (baseline and new) at the EOT visit (Day 84).
- Change from baseline in the percent of treatable warts (baseline and new) at the EOT visit (Day 84).
- Proportion of subjects exhibiting complete clearance of all treatable warts (baseline and new) at Treatment Visit 2, Treatment Visit 3, Treatment Visit 4.

Exploratory endpoints:

- Percent reduction of all treatable warts (baseline and new) from baseline at Treatment Visit 2, Treatment Visit 3, Treatment Visit 4.
- Change from baseline in the number of treatable warts (baseline and new) at Treatment Visit 2, Treatment Visit 3, Treatment Visit 4.
- Proportion of subjects exhibiting $\geq 50\%$ clearance of all treatable warts (baseline and new) at the EOT visit as compared to baseline.
- Proportion of subjects who respond to treatment defined by a $\geq 50\%$ reduction in total wart area at EOT visit compared to baseline.
- Proportion of subjects exhibiting reduction of at least 1 treatable wart from baseline at Treatment Visit 2, Treatment Visit 3, Treatment Visit 4 and at the EOT Visit.
- Proportion of subjects exhibiting complete clearance of all treatable warts (baseline and new) at follow-up visits on Day 105, Day 126 and Day 147.
- Percent reduction of all treatable warts (baseline and new) from baseline at follow-up visits on Day 105, Day 126 and Day 147.
- Change from baseline in the number of all treatable warts (baseline and new) from baseline at follow-up visits on Day 105, Day 126 and Day 147.

8.2. Baseline Values

Unless otherwise noted, baseline is defined as the last non-missing value recorded prior to the first application of study drug. When applicable, unscheduled visits will be used in the determination of baseline values.

8.3. Adjustments for Covariates

No statistical analysis is planned for this study; as a result, no adjustment for covariates will be made.

8.4. Handling of Dropouts or Missing Data

All subjects who receive treatment will be evaluated in the ITT population. In the event a subject requests to be removed from the study due to study related adverse events or additional spreading of disease, data will be collected and analyzed as a treatment failure and not replaced.

Unless described otherwise in subsequent sections, analyses will be carried out with the data available using no imputation for missing data. A description of how missing data as well as warts that combine will be handled for select endpoints is included below.

